1. ETDRS BCVA
2. Slitlamp biomicroscopy:
 - Dilated fundus examination with 78D Volk lens
 - Intraocular pressure by Goldmann applanation tonometry
3. Spectral domain OCT
4. Optical coherence tomography angiography if available on site.
5. Fundus photography and autofluorescence.

Study Treatments Schedules:

Laser:

- Pupillary dilatation: Will be achieved using Tropicamide 1% and Phenylephrine 2.5%. One drop instilled every five minutes repeated three times.
- Anaesthesia: Topical anaesthetic will be applied to the cornea, prior to the commencement of treatment.
- Lens: Area centralis contact lens will be coupled to the cornea with 1% methylcellulose or equivalent.
- Laser system: Pascal® laser with 532 nm (green) or 577 nm (yellow) wavelength, with EndPoint Management Software (EpM) at 30%, 200 μm spot diameter and 0.25 spot-width spacing. A grid-pattern treatment will be applied to the area of retinal thickening as per OCT. The total number of spots should exceed 500, including the full macula grid + plus patterns of 2x2 inside the grid and patterns of 3x3 or 4x4 outside the grid.

Arm A:

Patients will be treated initially (Day 0) and every 6 months during the follow up, if meet retreatment criteria.

- **Number of laser spots:** >500. Customized grid pattern to cover area of drusen.
- **Spot size:** 200 μm
- **Duration for titration:** 15 or 20 ms
- **Exposure:** Laser power will be titrated to produce a barely visible burn, considered a 100% at EpM®. For the treatment, energy is set at 30% to achieve non-damaging exposures.
- **Titration power range:** 100 to 200 mW
- **Spot spacing:** 0.25 spot-width-apart.
- **Retreatment criteria:**
 - Meet initial inclusion/exclusion criteria
 - Does not exhibit significant reduction in drusen volume 6 months after previous treatment. Significant is a 50% reduction in the cube root volume of drusen.

Arm B:

Patients will be treated with a sham laser (zero therapeutic power, only the aiming beam) and observed.

PATIENT FOLLOW-UP:

All participants will receive treatment at the initial treatment day and will have follow-up visits at 1 month (optional), 3, 6, 9, 12, 18, 24 months.

At the end of the 24 month period there will be an additional 3 year follow up. During the 3 year follow up, there would be no active component, the subjects will be seen once per year and undergo visual acuity testing and non-invasive retinal imaging to monitor for long term effects of treatment. This should not place a significant burden on the subjects since they are typically seen every 6 to 12 months for routine follow-up.

Best-corrected visual acuity (BCVA) using ETDRS charts at a distance of 4 meters, digital fundus photography, fundus autofluorescence, ocular coherence tomography (OCT), ocular coherence tomography angiography (OCTA when available on the site) will be carried out at baseline and at each follow-up visit.

TEST, treatment	Baseline	0	1 optional	3	6	12	18	24
Laser treatment		x			x	x	x	x
ETDRS visual acuity (BCVA)	x	x	x	x	x	x	x	x
Slitlamp	x	x	x	x	x	x	x	x
OCT	X	X	X	X	X	X	X	X
OCTA*	X	X	X	X	X	X	X	X
Digital Fundus Photography	X	X	X	X	X	X	X	X
Fundus autofluorescence	X	X	X	X	X	X	X	X

*OCTA will be done if available on site

STUDY RANDOMIZATION PROCEDURE

The subjects will be allocated to each arm of the study with simple randomization method using a computer-generated randomization list and sequentially numbered, sealed, opaque envelopes (SNSOE).

After a subject has signed informed consent, their name will be written on the selected envelope by the Clinical Trials Coordinator. The 56 eyes will

be randomly allocated to one of the two arms. The computer randomization will be done by the Clinical Trials Coordinator. The randomization table will be given to an independent person, who will sequentially label 56 envelopes, and enclose the written treatment type within the envelope. The study arm will be coded numerically for each subject.

METHOD OF STATISTICAL ANALYSIS

The data will be analysed using analysis of covariance, adjusting for baseline and disease severity. Results will be presented as differences between the treatment arms with their associated 95% confidence intervals, and non-significant effects interpreted in the context of these and the limited power of the study.

SAMPLE SIZE:

We estimated our sample size based on previous comparable publications that included approximately 50 eyes on average.¹¹⁻¹²

EFFICACY MEASURES:

Primary Outcome:

- Reduction in drusen volume in arm A compared to arm B.

Secondary Outcomes:

- Mean change in visual acuity (ETDRS letters)
- Mean change in average central retinal thickness (ACRT) after 12, 18, 24 months of follow up.
- The proportion of patients with ACRT < 300 µm on Spectral domain OCT after 12, 18, 24 months of follow up
- Conversion into GA or CNV

SAFETY MEASURES:

- Monitoring of adverse events (AEs) and serious adverse effects (SAEs) (the incidence of ocular AEs and SAEs).
- Assessment of the retinal autofluorescence to identify any laser burn.
- Signs of any laser burn identified at RPE-photoreceptors layers on DRI-OCT.

ADVERSE EFFECTS:

- Any medical incidence in patients who received laser that could be associated with the treatment delivered in the research study.
- Any temporal or transitory adverse effect that has relationship to the study therapy.

REPORTING ADVERSE EVENTS (AE) AND SERIOUS ADVERSE EVENTS

- With any AE, we will treat the SP as appropriate to prevent further complications and to potentially resolve the event.
- SAEs and AE will be reported immediately (when the subject is in the office, if possible or within 24 hours of learning of the event) to the principal investigator, study coordinator and sponsor. The SP subject will be referred for further medical treatment if required.
- Follow-up reports on AEs should indicate whether the AE is presumed to be device-related, or a result of other factors, and should be recorded on the Adverse Events Report. The Adverse Events Report should be completed each time the subject is seen during the management of the incident and at resolution of the incident.
- All AEs occurring from the time of written informed consent throughout the course of the study (end of study is defined as the end of the scan acquisition) will be recorded at the study site.
- The AE should be made to describe it in terms of a diagnosis. If a clear diagnosis has been made, individual signs and symptoms will not be recorded unless they represent atypical or extreme manifestations of the diagnosis, in which case they should be reported as separate events. If a clear diagnosis cannot be established, each sign and symptom must be recorded individually.

All the adverse events shall be recorded in detail as specified below:

Name (Type)	The common name of the adverse event that appeared shall be written down.	
Date of onset	The first date that the physician in charge found the adverse event shall be written down.	
Causal relation	Write down probable causes, and classify the causal relation with the test device depending on the presence or absence of the causal relationship as defined below. The adverse events that are judged to have no relation with the test devices are classified as complications; all the others are classified as adverse device effects.	
	Probably not related	The adverse event is definitely related to other than the test device. (Complication)
	Possibly related	The adverse event is possibly related to the test device; the causal relationship with the test devices is fully undeniable. (Adverse device effect)
	Probably related	The cause of the adverse event cannot be located. However, the adverse event is probably related to the test device. (Adverse device effect)
	Definitely related	The adverse event is definitely related to the test device. (Adverse device effect).
Severity	The severity shall be classified into mild, moderate and severe based on the criteria:	
	Mild	The symptom is mild and expected to heal soon.

	Moderate	The symptom is described as neither mild nor severe.
	Severe	The finding is serious and expected to interfere with the subject's daily life depending on the subject's physical predisposition or the circumstances under which the adverse event appeared.
Symptom, progress and treatment	Necessity for treatment and progress from the detection of the adverse event and the determination of outcome shall be written down.	
Outcome	The classification into "healed", "unchanged", "aggravated", or "death" and the outcome date shall be written down. If the subject died, statement of death shall be made.	
Views on the adverse event	Views on the adverse event by the physician in charge shall be written down. Omission is allowed if there are no special comments.	

POTENTIAL RISKS:

- Complications of conventional laser therapy including marked vision loss, paracentral scotomas or accidental application of laser in the fovea. There is limited data regarding potential risks of photothermal therapy, however, due to its non-damaging nature, it is expected to be safer than conventional photocoagulation.

STUDY PATIENT DISPOSITION

Completed SP: A completed SP is one who has not been discontinued from the study and has completed all study related procedures.

Discontinued SP: SP may be discontinued prior to their completion of the study due to:

- subject request
- adverse events
- protocol violations
- administrative reasons (e.g., inability to continue, lost to follow up)
- termination of the study

Note: In addition, any SP may be discontinued for any sound medical reason. Notification of a SP discontinuation and the reason for discontinuation will be clearly documented.

STUDY TERMINATION

The study may be stopped at any time by the investigator, the sponsor, and/or study monitor with appropriate notification.

STUDY COMPLIANCE

An investigator should not deviate from the clinical protocol. Should a deviation occur the date of and reason for deviations will be documented by the monitor via the monitoring report and further detail may be requested from the investigator. Deviations will be reported to the sponsor immediately.

MONITORING AND QUALITY ASSURANCE

Study Monitoring

The designated study monitor will review the protocol, regulatory obligations, and other material or equipment relevant to the conduct of the study prior to the start of the study with the principal investigator/co-investigator(s) and pertinent study staff. Monitoring visits will occur as necessary during the course of the investigation to verify:

- The rights and well-being of subjects are protected.
- The conduct of the investigation is in compliance with the currently approved protocol.
- The integrity of the data.
- Device accountability adequate study documentation.

CONFIDENTIALITY

Recording of Data

SP data recorded during the study will be documented in the patient's clinical file. In the data analysis the SP will only be identified by the subject number, and by their initials if also required. If, as an exception, it is necessary for safety or regulatory reasons to identify the SP, the sponsor or its representative, and the investigator are bound to keep this information confidential.

All personal SP data collected and processed for the purposes of this study will be maintained by the investigator and his staff with adequate precautions as to ensure that the confidentiality of the data in accordance with local laws and regulations.

PUBLICATION POLICY

Authorship and manuscript composition will reflect cooperation among all parties involved in the study. Authorship will be established before writing the manuscript.

REFERENCES

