Micropulse laser photocoagulation avoids the excessive heating which causes visible burns, tissue necrosis, and related collateral effects¹³, while providing similar clinical benefits as conventional laser coagulation.¹⁴⁻¹⁹ However, the lack of a reliable titration for every patient and absence of visible endpoint makes it difficult for the physician to (a) know which retinal areas have been treated and (b) to ensure the adequate amount of laser energy in the treatment. In addition, the dense coverage of the retina with the sub-visible laser exposures typically requires more than 500 spots in the macula, which is difficult to accomplish without pattern scanning laser. These issues prevented acceptance of this technology in clinical practice.

We have developed the titration protocol for PASCAL laser, which ensures that pulse energy is within the range of clinical efficacy, but does not exceed the tissue damage threshold²¹ in every patient. This protocol, called EndPoint Management, has been recently tested in a clinical trial, which demonstrated its safety and efficacy in treatment of Central Serous Retinopathy²² using 30% energy settings. The trial demonstrated lack of tissue damage and excellent tissue response to the treatment, even after multiple retreatments. The average retreatment period in this trial was found to be 6 months.

We propose to use the same laser parameters for treatment of the macula in patients with early AMD to prevent drusen growth and advancement of the disease into geographic atrophy or neovascularization.

AIMS OF THE STUDY

1. To determine whether photothermal therapy (PTT) of the macula with EpM® reduces the volume of drusen in the macula.
2. To determine whether PTT decreases the incidence of advanced AMD (neovascular AMD or geographic atrophy).

The primary efficacy outcome measure will be the reduction in drusen volume in the central 3mm circle over 12, 18, 24 months in subjects treated with PTT, compared to observation alone.

The secondary efficacy outcomes after the month 12, 18, 24 of follow up will be:

- **Functional outcome:**
 - Mean change in visual acuity in both groups.
- **Anatomical outcome:**
 - Reduction of drusen growth;
 - Prevention of neovascular AMD;
 - Prevention of geographic atrophy based on OCT and FAF.

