The treatment will be randomised at this stage, and the SP will be allocated to arm A (treat) or arm B (observe). The 56 eyes will be randomly allocated to each of the two study arms, 28 in each arm. The SP will be given a trial number, and the treatment record will be coded. **For patients where both eyes meet eligibility criteria both eyes will be enrolled with the Right Eye randomly assigned to active treatment arm or sham arm, with the Left Eye assigned to the opposite arm.**

3. Treatment Visit:

The SP will undergo treatment within 14 days after the examinations are performed.

Patient-eligibility

Inclusion criteria:

1. Older than 60 years of age.
2. Male or female patients with nonexudative AMD with a drusen volume of at least 0.03mm³ on OCT within the central 3mm circle centered on the fovea.
3. Adequate pupil dilatation and clear media to perform color, red-free imaging, fundus autofluorescence imaging, and OCT imaging.
4. Able to give an informed consent.

Exclusion criteria:

1. Presence of signs of advanced AMD, such as CNV, haemorrhages or macular atrophy based on OCT and FAF.
2. Previous macular laser treatment.
3. Any previous ocular condition that may be associated with a risk of developing macular oedema.
4. Vitreomacular traction determined clinically and /or by OCT, which in the opinion of the investigator contributes to the macular oedema (associated or causing a detachment of the fovea).
5. Presence of other macular disease such as epiretinal membrane, macular telangiectasia.
6. Ocular or periocular infections.
7. Planned intra-ocular surgery within one year.
8. Patient is unavailable for follow-up visits.

Study Examination Procedure

Baseline:

1. Full patient history including age, gender, ethnic group, diabetes history, medical history, medication history, ocular history, driving history, smoking status.

Baseline and Follow-up visits (see table):

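### Two Arm A treatment rules conflict with other protocol text: the area to be treated (thickening or drusen), and a retreatment criterion that, read literally, no treated eye can meet

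*Combined protocol and SAP*

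**What the plan says.** **Treated area.** In the combined protocol and SAP, the Laser paragraph of Study Treatments Schedules states: "A grid-pattern treatment will be applied to the area of retinal thickening as per OCT". The Arm A list in the same section gives the target as: "Customized grid pattern to cover area of drusen". Inclusion criterion 2 under Patient-eligibility admits "Male or female patients with nonexudative AMD with a drusen volume of at least" 0.03 mm³ on OCT "within the central 3mm circle centered on the fovea". Retinal thickening is not among the inclusion criteria.

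**Retreatment.** Arm A eyes are treated on Day 0 and then every 6 months, provided that they meet the retreatment criteria. There are two criteria. The first is "Meet initial inclusion/exclusion criteria". The second is the lack of a significant reduction in drusen volume 6 months after the preceding treatment. Exclusion criterion 2 bars eyes with earlier laser treatment of the macula and makes no exception for laser given within the study. The laser row of the visit table under Patient Follow-up is marked at 0, 6, 12, 18 and 24 months.

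**The concern.** These lines tell the operator where to place the laser and tell the site when to repeat it. Together they define what is compared with sham.

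On area, the two instructions name different anatomical targets. In an eligible eye without thickening, the first names nothing to treat and the second does. Extent of treatment also matters to the trial's own argument: the Introduction suggests that earlier subthreshold laser may have failed to slow progression because only a few tens of spots were applied, and offers denser treatment as the remedy. A protocol built on that idea should say consistently where the spots go.

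On retreatment, the condition for a second session appears to be one that the first session makes impossible to meet. Sites then have to decide for themselves which of the initial criteria still count. A reader of the results could not tell from the protocol alone which area was treated, or which rule decided how many sessions an Arm A eye received.

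**Working it through.** The plan states no figure on this point and none is needed. The check sets the texts side by side.

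**Treated area**

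1. Laser paragraph: the target is thickened retina, identified on OCT.
2. Arm A list: the target is the area occupied by drusen.
3. Entry: drusen volume of at least 0.03 mm³ in the central 3 mm circle. No inclusion criterion mentions thickening, and exclusion 3 removes eyes with a previous condition that carries a risk of macular oedema.
4. From 3, an eye can be eligible with no area that fits 1. It will have drusen, so it will have an area that fits 2.
5. No sentence ranks 1 above 2, defines thickening in terms of drusen, or limits either instruction to some of the eyes.

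The two instructions therefore cannot both be followed in every eligible eye.

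**Retreatment**

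| Source | What it implies at month 6 for an Arm A eye treated on Day 0 |
|---|---|
| Retreatment criterion 1 | The eye must satisfy the initial inclusion and exclusion criteria |
| Exclusion 2 | An eye with earlier macular laser is excluded; study laser is not exempted |
| Retreatment criterion 2 | Presupposes that the eye has been treated before |
| Arm A schedule | Laser every 6 months if the criteria are met |
| Visit table, laser row | Laser marked at 6, and again at 12, 18 and 24 |

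1. Every Arm A eye treated on Day 0 has had macular laser by month 6.
2. By exclusion 2, read as written, it no longer satisfies the initial criteria.
3. By criterion 1 it then cannot be retreated at month 6. The same holds at 12, 18 and 24.
4. Criterion 2 would have no use, and the four later laser marks in the table could never apply.

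The conditional wording of the schedule does not remove the conflict, because the condition is the part that cannot be met literally. Nor can criterion 1 simply be passed over: it also carries the drusen-volume threshold and the exclusion of eyes with signs of advanced AMD into the retreatment decision. The open question is which of the initial criteria are meant to apply again.

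**The case against.** The best case for the plan is that a sensible reader can see what was meant. Exclusion 2 sits under eligibility, which is assessed before any study laser, so earlier laser naturally means laser before enrolment. Criterion 1 speaks of the initial criteria and most plausibly asks whether the eye still qualifies on disease status. A reading that empties the retreatment section and four table entries is not one that a site would be expected to follow. On area, the drusen-based entry criterion and the drusen-volume outcome fit the Arm A list, so the reference to thickening may be loose wording. Much of this stands: it limits the practical effect. It does not make the texts agree, because no sentence supplies the exemption or says which area description governs.

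Four stronger readings are tempting, and the documents do not support them.

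- **A third target.** The Laser paragraph continues: "The total number of spots should exceed 500, including the full macula grid". A reader might count this as a third description of the area. It is an item in the spot count, followed by small patterns added inside and outside the grid, and is compatible with a grid customised to drusen. The firm conflict is thickening against drusen.
- **Settling the area from the spot count.** A reader might try to convert more than 500 spots at the stated size and spacing into an area. That requires a single, non-overlapping, uniform lattice. The paragraph describes a composite pattern and does not say whether its parts overlap, so the result would not decide between the two descriptions.
- **Retreatment forbidden.** A reader might infer that Arm A eyes will receive only one session. Criterion 2, the schedule and the table all show that retreatment was intended.
- **Every retreatment a deviation.** A reader might infer that each repeat session must be reported under Study Compliance. That follows only from the literal reading, which was evidently not meant, and nothing in the documents shows that sessions would be logged that way.

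**Conclusion.** Both contradictions are present in the text, and confidence in that is high. They are conflicts between stated rules, not missing detail: one between two descriptions of the treated area, the other between retreatment criterion 1 (through exclusion 2) and the rest of the retreatment provisions.

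The size is modest. No numerical effect on the estimate, its precision or safety is claimed, and the documents give no basis for one: they report neither the extent of drusen or thickening per eye nor the sessions delivered. The randomised comparison with sham remains valid for whatever Arm A treatment is delivered. What suffers is the definition of that treatment and a reader's ability to know what was compared. The conclusion assumes only that eligibility is as listed and that no unpublished instruction to sites resolves the wording. It is a point for the sponsor to consider, not a threat to the trial.

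**What to change.** Amend the protocol in two places.

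1. In Study Treatments Schedules, make the Laser paragraph and the Arm A list give the same description of the treated area.
2. Reconcile exclusion 2, the retreatment criteria and the visit table, and state which of the initial inclusion and exclusion criteria apply at retreatment.

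If eyes have already been treated, state in the report which reading was followed on each point, and give the number of laser sessions per Arm A eye.

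The choice of area and of retreatment rule is a clinical matter for the sponsor and investigators; none is proposed here. The cost is amended wording and a short statement in the report, with no extra patients or procedures.

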- **Safety Assessments.** Safety of the treatment will be assessed for ocular adverse event incidence (AEs) and serious AEs (SAEs), based on the reports of the patients and examination during or between visits until the month 24 of follow up. After 24 months, subjects will then be followed for an additional 3 years for observation
- **Serious adverse events (SAEs)** will be monitored continuously.

STUDY METHODS

Design:

- Prospective, Randomized Clinical Trial (RCT).
- 24 months with an additional 3 year observation follow up period. Subjects will be seen once a year and undergo non-invasive testing.
- Total patient recruitment 56 patients.
- Number of arms: 2 arms.
- Number of patients: 28 patients in each arm.

Patient Recruitment

1. Initial Assessment

The study will enroll 56 eyes in total. Patients will be initially assessed as part of their standard management and, if fulfilling all the inclusion criteria, will be referred to a Study Investigator.

At the initial assessment, the investigator will confirm that the patient has satisfied the eligibility criteria stated in the Study Protocol (SPR) and the study will be discussed in full with the study participant (SP). If interested in participating, the SP will be given a written informed consent to take home for further consideration. The patient will have a minimum of 24 hours to decide whether or not to take part in the study. All study procedures, will be explained to the SP by the investigator or staff member. The nature of the study will be also explained to the SP together with hazards of the study procedures, including any possible adverse events. The SP will be informed that he or she is free to terminate participation in the study for any reason.

Any patient unwilling to participate at this stage will be managed as part of the appropriate routine eye care pathway.

The study patient will undergo the Examination Procedures at the Baseline visit. The data from these tests will be used for study data analysis.

2. Examination Procedures at Baseline and Follow-up visits

- (1) ETDRS best corrected visual acuity.
- (2) Slit lamp biomicroscopy: dilated fundus examination with 78D Volk lens, intraocular pressure by Goldmann applanation tonometry.
- (3) Spectral domain OCT (Cirrus SD-OCT): Macular/macular cube/Volume scan & average central retina thickness and Drusen volume.
- (4) Fundus photography and autofluorescence.

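### The coordinator who generates the randomisation list also handles the envelopes at enrolment, so the sealed envelopes do not conceal the sequence from that role

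*Combined protocol and SAP*

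**What the plan says.** STUDY RANDOMIZATION PROCEDURE describes simple randomisation from a computer-generated list, concealed in opaque, sealed envelopes numbered in sequence. It gives three tasks to two roles:

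- **Generating the list:** "The computer randomization will be done by the Clinical Trials Coordinator".
- **Preparing the envelopes:** "The randomization table will be given to an independent person, who will sequentially label 56 envelopes, and enclose the written treatment type within the envelope".
- **Handling an envelope at enrolment:** once the subject has signed consent, "their name will be written on the selected envelope by the Clinical Trials Coordinator".

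Three other places bear on the point:

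- Patient Recruitment, 1. Initial Assessment: "the investigator will confirm that the patient has satisfied the eligibility criteria stated in the Study Protocol".
- The randomisation paragraph that follows the baseline examinations, for patients with two eligible eyes: "Right Eye randomly assigned to active treatment arm or sham arm, with the Left Eye assigned to the opposite arm".
- METHOD OF STATISTICAL ANALYSIS: "The data will be analysed using analysis of covariance, adjusting for baseline and disease severity".

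**The concern.** Allocation concealment requires that nobody who handles entry into the trial can know the next assignment. Here one role stands at both ends of the chain. An opaque envelope cannot hide a sequence from the person who produced it, and having someone else fill the envelopes afterwards does not change that.

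The stake is selection bias. A role that knows the next assignment has an opportunity to influence whether, or when, a particular patient is entered. Sham treatment does not protect against this, because it begins after allocation. The covariance adjustment protects only to the extent that baseline and disease severity capture whatever guided the choice. With 28 eyes per arm, a handful of steered entries could be visible in the result.

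**Working it through.** **Tracing the tasks**

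1. The coordinator runs the randomisation, so the list exists in that role's hands first.
2. The table then goes to an independent person, who labels and fills 56 envelopes. The text does not say that the coordinator keeps a copy. Nor does it say that the coordinator is kept from seeing the output, or is replaced by someone else at enrolment.
3. After consent, the coordinator writes the name on the envelope.
4. Eligibility is confirmed by the investigator. No section gives the coordinator a part in referral or eligibility.

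Steps 1 and 3 fall to the same role, and no other section separates them. Someone who has seen the list can foresee 56 of 56 assignments. Under concealed simple randomisation, guessing gives 56 × 0.5 = 28 on average.

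**What foreknowledge could do.** Sequential numbering points to use in order. Under ordered use, the only routes left are whether and when the next patient is entered. The same holds for a patient with two eligible eyes: the next envelope fixes the right eye's arm, and the left eye takes the other.

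**Illustration of size.** The plan states no figure to reproduce. The documents give 28 eyes per arm. Everything else here is assumed: k = 1 to 3 swaps, all in the same direction; eyes d = 0.5 or 1 SD apart in prognosis; single-eye patients; no true effect. A swap means that two eyes exchange arms, as when two patients with opposite pending assignments change places in the order of entry.

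- Each swap moves each arm mean by d/28 in opposite directions, so shift = 2kd/28 SD. For k = 3, d = 1: 6/28 = 0.214 SD.
- Unadjusted standard error = √(2/28) = 0.267 SD. The 95% interval half-width = t(0.975, 54 df) × 0.267 = 2.005 × 0.267 = 0.536 SD.
- Error rate: two-sided 5% test, noncentral t, noncentrality = shift / standard error, 54 df. For k = 3, d = 1: 0.214/0.267 = 0.80, which gives 12.35%.
- If the covariates capture half of the steered prognosis, the shift halves. The standard error becomes √(2(1 − R²)/28), with 52 df. R² is the share of outcome variance that the covariates explain, assumed to be 0.25 or 0.50, giving standard errors of 0.231 and 0.189 SD.

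| d (SD) | k | Shift, none captured (SD) | Error, none captured | Shift, half captured (SD) | Error, half captured (R² 0.25 to 0.50) |
|---|---|---|---|---|---|
| 0.5 | 1 | 0.036 | 5.2% | 0.018 | 5.1% to 5.1% |
| 0.5 | 2 | 0.071 | 5.8% | 0.036 | 5.3% to 5.4% |
| 0.5 | 3 | 0.107 | 6.8% | 0.054 | 5.6% to 5.9% |
| 1 | 1 | 0.071 | 5.8% | 0.036 | 5.3% to 5.4% |
| 1 | 2 | 0.143 | 8.2% | 0.071 | 6.1% to 6.6% |
| 1 | 3 | 0.214 | 12.3% | 0.107 | 7.4% to 8.6% |

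If the covariates capture all of the steered prognosis, the shift is zero and the error rate stays at 5%. No error rate is given for patients with two study eyes, because the plan does not state how paired eyes are analysed.

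**The case against.** The strongest defence is that the plan already has real safeguards and shows no route to harm. The envelopes are numbered, sealed and opaque. An independent person fills them, and a name goes on only after consent. The table is said to be handed over, and reading a retained copy into that is an argument from silence. The investigator, not the coordinator, confirms eligibility. The planned adjustment covers baseline and disease severity, the features on which steering would most naturally occur.

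Much of this stands. It lowers the likelihood of steering, and it means that the adjusted part of the table is nearer to the plan than the unadjusted part. It does not restore concealment: whoever ran the list could have seen it, whether or not a copy was kept, and that role is still present at enrolment.

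Three stronger readings are tempting, and the documents support none of them.

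- **That allocation was subverted.** The text shows an opportunity, not its use.
- **That the coordinator could pick an envelope, and so decide which eye of a two-eye patient is treated.** This would need envelopes used out of order, and sequential numbering argues against that. The reference to a selected envelope is too thin to establish it.
- **That the trial's error rate is 12%.** That is the most extreme cell of an assumed grid. It requires three swaps, all in one direction, on prognosis that the coordinator can recognise and the covariates miss entirely.

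**Conclusion.** The point holds as a weakness in role separation. By the plan's own wording, the sequence is not concealed from the one role that both generates the list and handles the envelopes. Confidence is high on that textual fact.

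The size of any bias cannot be derived, because the documents give no number of swaps, no outcome SD and no covariate R². Under the assumptions above, the two-sided error rate runs from about 5.2% to 12% with nothing captured, from 5.1% to 8.6% with half captured, and is 5% with everything captured. In the half-captured grid only three swaps at 1 SD exceed 6.6%. These figures show why a small trial should close the gap. They are not an estimate of what happened. The case for changing the plan rests on the plain text and the low cost of the remedy, and on the fact that concealment lost at allocation cannot be fully repaired at analysis.

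**What to change.** Have the independent person who already fills the envelopes also generate and hold the list. That person must be able to run the randomisation and take no part in recruitment. The coordinator should receive only sealed envelopes. These should be assigned and opened in strict number order, after consent and eligibility are recorded, with each assignment entered in a dated log.

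The cost is one task moved to a person already in the plan, a log sheet and a few sentences of protocol text. If envelopes have already been prepared, the unused ones would need to be re-made from a new list. No extra patients are needed.
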